15. APPENDICES

15.1 Survey: Questions for pre-registration

1. Please select your country (*Denmark; France; Germany; Italy; The Netherlands; Poland; Spain; United Kingdom*)
2. Please select your age category (*25-34; 35-44; 45-54; 55-64; 65 or older*)
3. Please select your sex (*male; female; other*)
4. Please select your profession (*general practitioner; palliative care specialist; nursing home physician; geriatrist; vascular medicine specialist; oncologist; haematologist; pulmonologist; cardiologist; neurologists; vascular surgeon*)
5. Please select the professional experience group that matches your years of experience (*< 5 years; 5-10 years; 11-15 years; 16-20 years; 21 or more*)
6. Please provide an estimate on the number of patients you see/treat with active cancer each year, who are considered to be in end-of-life care.
This number is important for the upcoming data collection.

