7. COUNTRIES INVOLVED

The survey will be conducted among healthcare professionals mainly from the eight European countries represented in the SERENITY consortium:

- Denmark
- France
- Germany
- Italy
- The Netherlands
- Poland
- Spain
- United Kingdom

Due to promotion of the project via international networks and social media (s. section 10), we also expect participants from other countries and regions. Depending on the number or proportion of participants from outside Europe, these will be evaluated separately.

8. (TARGETED) NUMBER OF SUBJECTS

The study aims to generate data from a total of at least 800 healthcare professionals (i.e., either 100 each from the countries listed in section 7 or corresponding participant numbers from additional countries) and up to 2400 anonymised patients, considering that each healthcare professional will be asked to describe actual decisions and anonymous data obtained from medical charts in one to three consecutive patients meeting the definitions below at the time of consideration.

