9. SAMPLE SIZE CONSIDERATIONS

In view of the FMR design, there is no formal predetermined sample size. In principle, a successful FMR should include a large sample size for reliable and generalizable conclusions.³

For DCE, the required sample size (N) depends on the number of choice tasks (t), the number of alternatives (a), and the number of analysis cells (c) according to the following equation: $N > 500c/(txa)$. Where DCE studies usually require only 100 responses, the minimum sample size to show that deprescribing ATT in a certain setting is preferred over continuing the ATT with a statistical power β of 80% and a 2-sided significance level α of 0.05 is 190. This is well below the planned number of 800 observations.⁴

We will monitor the number of preregistered participants and adjust the recruitment plan based on the actual accrual.

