10. DESCRIPTION OF STUDY PROCEDURES

The study will be divided into three phases: the recruitment phase, the FMR-phase and the data analysis phase.

In the **recruitment phase**, the national coordinators of the project group will advertise the study through traditional professional networks as well as their social media channels. Information about the study will be distributed via personal communication, relevant scientific organisations and journals, and via social media. The healthcare professionals of interest will be invited to pre-register for study participation so they can be assigned a unique link to the electronic case report forms (eCRF). During the preregistration, characteristics of the pre-registrants will be checked (i.e., sex, age, profession, years of experience, the country where they are practicing, and the number of cancer patients in palliative care whom they care for on a yearly basis).

In the **FMR phase**, all preregistered participants will be asked simultaneously to complete the survey using the *Castor electronic data capture platform* within seven days.

The survey will be divided into the following sections:

- a) **General questions** regarding end-of-life care (e.g., "When do you consider a patient in end-of-life care?") and (de)prescription of antithrombotic medication to cancer patients during end-of-life care (e.g., "Have you ever considered deprescribing antithrombotic medicine?").
- b) A sequence of **choice scenarios** i.e., hypothetical scenarios that vary with regard to several characteristics (**attributes**; e.g., bleeding risk, thrombotic risk). Attributes will be further specified by varying choice levels (**attribute levels**; e.g., low or high bleeding risk), which are considered relevant for the decision on continuation or stopping antithrombotic medication in the patient population studied. In accordance with the discrete choice experiment (DCE) methodology, participants will be asked to select the healthcare intervention (i.e., either continuation or discontinuation of the antithrombotic therapy) that in their opinion would benefit the patient the most within each choice set.
- c) Participants will be asked to share **actual case decisions** they made in a maximum of three consecutive cases involving patients with active cancer, who were considered to receive end-of-life care. Fully anonymised data of the patients (sex, age category, primary tumour, tumour

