11. REGULATORY AND LEGAL REQUIREMENTS

As confirmed by the responsible ethics committee, due to the non-interventional nature of this study and since no personal data of patients will be recorded or processed, professional advice and/or submission of this protocol to the ethics committee before commencement of the survey is not required.

Data privacy of participating healthcare professionals will be taken into account in accordance with the European General Data Protection Regulation (GDPR). With the exception of the e-mail addresses of survey participants for the purpose of forwarding the survey link and information on survey launch and completion, no personal data will be stored or processed. As detailed in the information for prospective participants, participants implicitly consent to the use of their e-mail addresses for said purposes by pre-registering.

Data on patients will be sufficiently coarsened such that no identification will be possible. As an additional security measure, this part of the survey will be exported and analyzed separately from the other two sections (s. section 9 above).

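### The only country question offers eight countries and no 'other', so the number of participants from outside Europe, on which Section 7 bases an analysis decision, cannot be obtained

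*Combined protocol and SAP*

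**What the plan says.** Appendix 15.1, question 1, is a closed list: "Please select your country (*Denmark; France; Germany; Italy; The Netherlands; Poland; Spain; United Kingdom". These are the eight consortium countries named in Section 7, one for one.

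Section 7 looks beyond those eight. Because the project is promoted through international networks and social media, "we also expect participants from other countries and regions". It then attaches an analysis decision to them: "Depending on the number or proportion of participants from outside Europe, these will be evaluated separately".

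Section 8 allows the target of at least 800 professionals to be made up of "either 100 each from the countries listed in section 7 or corresponding participant numbers from additional countries".

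Section 10 makes pre-registration the way in. Professionals are "invited to pre-register for study participation so they can be assigned a unique link to the electronic case report forms", and among the characteristics checked at that step is "the country where they are practicing".

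Section 9 adds: "We will monitor the number of preregistered participants and adjust the recruitment plan based on the actual accrual".

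**The concern.** The plan expects participants from outside the eight countries, may count them towards its target and may analyse some of them apart. The one item that records country has no answer that is true for them.

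At stake is the input to the Section 7 decision. Without the number from outside Europe, nobody can judge whether that group is large enough to set apart. The first objective in Section 4 is to describe European practice, and the Background (Section 3) says that deprescribing may differ widely between countries. Whether an answer comes from inside or outside Europe therefore bears on what the results mean.

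The point concerns the general questions and the discrete choice experiment. For the case data, Section 11 says that "this part of the survey will be exported and analyzed separately from the other two sections", and nothing in the documents attaches a country to a case.

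**Working it through.** **1. The plan's own figures.** 8 countries × 100 = 800 professionals, and 800 × 3 cases = 2400 patients. Both agree with Section 8. The defect does not affect this arithmetic.

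**2. Is country recorded anywhere else?** Appendix 15.2 (general questions), 15.3 (choice scenarios) and 15.4 (case decisions) contain no country item. Question 1 of 15.1 is the only source.

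**3. Could the list be illustrative, or an open answer implied?** Appendices 15.2.1 and 15.3 are headed as examples; 15.1 is not. Where an open answer is wanted, it is written out: question 3 of the same form includes 'other', and several items in 15.4 offer free text. The printed list is best read as the list.

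**4. What can an unlisted participant do?** There are three possibilities, and the documents do not say which applies.

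| Behaviour | Counts for the eight countries | Number from outside Europe | Pooled European results |
|---|---|---|---|
| Blocked at registration | Correct | Not observed; these people are absent | No shift |
| Item left blank | Correct | Unknown; mixed with other Europeans and ordinary non-response | Depends on whether blanks are pooled |
| Wrong country chosen | Contaminated | Unknown | Non-European answers enter |

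In every row the number that Section 7 needs is unavailable.

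**5. How large could a shift be? (illustration only)** The documents give neither the share of non-Europeans nor any difference in their answers. Assume a non-European share *s* of 5% to 20% of 800, all of them misfiled, and a difference *d* of 20 percentage points on a yes/no item.

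- Number affected: 0.05 × 800 = 40; 0.20 × 800 = 160.
- Shift in the pooled percentage = *s* × *d*: 0.05 × 20 = 1 point; 0.20 × 20 = 4 points. With *d* = 10: 0.5 and 2 points.
- 95% half-width at a proportion of 0.5: 1.96 × √(0.25/800) = 3.46 points.
- Share at which the shift equals the half-width: 3.46/20 = 17.3%, or 139 of 800 (rounded up). With *d* = 10 it is 3.46/10 = 34.6%, outside the assumed range.
- The shift is 0 if these people are blocked, or if all unlisted participants come from other European countries.

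If single-country results were reported and 40 participants misfiled, an even spread would put 40/8 = 5 in each group of 100, a shift of 0.05 × 20 = 1 point. If all 40 chose the same country, the shift there would be 0.40 × 20 = 8 points. The half-width at n = 100 is 1.96 × √(0.25/100) = 9.8 points.

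**6. How much of the shift is the form's doing?** Section 7 makes separate evaluation conditional and gives no threshold. Below whatever threshold is applied, non-European answers would apparently stay in the pooled results even with a perfect country question. The form causes the shift only where the true share would have triggered separation and the form hides it.

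**The case against.** The strongest defence is that the harm is small and conditional. Section 7 says participants come mainly from the eight countries. Recruitment is adjusted to accrual (Section 9), so 800 can be reached without anyone else. The live electronic form may also differ from the appendix. Under the assumptions above, the pooled shift stays below its own 95% half-width until more than 17.3% of respondents are both non-European and misfiled. Much of this stands, and it limits what can be claimed. It does not remove the mismatch: the documents mention no different live form, and the Section 7 decision still lacks its input.

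Four stronger readings are tempting, and the documents do not support them.

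- A reader might infer that the target of 800 is at risk. It may well be met from the eight countries alone.
- A reader might infer that the whole split by country is lost. With blanks it is not: the eight listed countries keep correct counts, and only the make-up of the blank group is lost.
- A reader might infer that the European results will be biased by 1 to 4 points. Those figures rest on assumed shares, differences and complete misfiling, and part of any shift could arise under Section 7 even with a correct form.
- A reader might infer that single-country results are compromised. Section 13 refers to predefined subgroups without naming country, so this harm arises only if such results are reported. The 8-point figure also needs every misfiled participant to choose the same country.

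It might also be said that country could be queried afterwards. No section provides for that. Section 11 limits the use of e-mail addresses to sending the link and information on launch and completion.

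**Conclusion.** The point holds as an internal inconsistency between Appendix 15.1 and Sections 7, 8 and 10. Followed as printed, the plan cannot obtain the number or proportion of participants from outside Europe, so it cannot carry out the decision that Section 7 ties to that figure. This conclusion comes from the text alone and needs no numerical assumption, only that the form is used as the appendix prints it.

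The further consequences depend on behaviour that the documents leave open, and their size is unknown. The study is not invalidated, but the form should be corrected, because a stated part of the plan otherwise cannot be executed.

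**What to change.** Before pre-registration opens, add two answers to question 1 of Appendix 15.1: 'other European country (please specify)' and 'country outside Europe (please specify)'. Together they give the count that Section 7 needs and let additional countries be counted as Section 8 allows.

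If pre-registration is already open, correct question 1 for new registrants and repeat the corrected item at the start of the survey (Appendix 15.2) for those already registered. This recovers the true country of participants who left the item blank or chose a wrong one. It cannot recover people already turned away, because they hold no survey link.

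The cost is two answer options and the coding of typed country names. No target or analysis method changes.

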15.2 Survey: General questions

1. When do you consider a patient in end-of-life care? If the life expectancy is:
A. < 1 year B. < 6 months C. < 3 months D. < 2 weeks
2. When a patient is considered to be in end-of-life care, I **XXX** prescribe antithrombotic medication upon the diagnosis of a thrombotic complication.
A. never B. sometimes C. often D. always
3. Have you ever deprescribed (i.e., terminated) antithrombotic medication in end-of-life care of cancer patients?
A. no B yes

In case of no, the participant will not be redirected to certain questions.

4. When a patient is considered to be in end-of-life care, I **XXX** deprescribe antithrombotic medication.
A. never B. sometimes C. often D. always
5. Give an estimate of the frequency per year that you consider deprescribing antithrombotic medication in patients, considered to be in end-of-life care:
XXX /year
6. Give an estimate of the frequency per year that you actually deprescribed antithrombotic medication in patients considered to be in end-of-life care:

XXX /year

7. Do you discuss deprescription of antithrombotic medication in patients at the end of life with colleagues?
A. never B. sometimes C. frequently D. always
8. Please indicate what factors determine whether you prescribe antithrombotic medication in patients considered to be in end-of-life care.
9. Please indicate what factors determine whether you deprescribe antithrombotic medication in patients considered to be in end-of-life care.

15.2.1 Examples of factors relevant to questions 8 and 9

1. Antithrombotic medication:
 - DOAC or VKA
 - LMWH (therapeutic)
 - Antiplatelet agent
2. Indication for antithrombotic medication:
 - Atrial fibrillation
 - Treatment of acute VTE event or prevention of (recurrent) VTE
 - Mechanical heart valves
 - Other indication
3. Bleeding risk:
 - Low
 - High
4. Thrombotic risk:
 - Low
 - High
5. Sex:
 - Female
 - Male
 - Other
6. Age:
 - < 40 years
 - 40-75 years
 - > 75 years
7. Patient's performance status:
 - Eastern Clinical Oncology Group performance status (ECOG-PS) grade 0-2
[Oken MM et al. Am J Clin Oncol. 1982]
 - ECOG-PS grade ≥ 3
8. Patient prognosis:
 - < 6 months
 - < 3 months
 - < 2 weeks

9. Patient preference:

- Stop antithrombotic treatment
- Continue antithrombotic treatment

10. Other

Free text

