2.2 End-of-life care

A patient is considered in end-of-life care in case of a confirmatory negative response of the healthcare professional to the question “Would you be surprised if this patient died in the next 6-12 months?”, which is an accurate and widely used trigger for referring a patient to specialist palliative care.^{1,2}

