4. STUDY OBJECTIVE(S)

- >To explore and describe current European practice patterns with regard to the use of ATT in end-of-life care of cancer patients following 'flash mob research (FMR)' methodology.
- To evaluate and understand the processes and factors that inform decisions concerning the deprescription of ATT in the last year of life of cancer patients receiving ATT via a discrete choice experiment (DCE) among healthcare professionals, who deal with end-of-life care in cancer patients, or prescribe such medication to cancer patients.

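### Seven of the nine general questions (section 15.2, items 2 and 4 to 9) leave out the restriction to cancer patients, so their population is ambiguous and may differ by profession

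*Combined protocol and SAP*

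**What the plan says.** The first objective (section 4) is to describe "current European practice patterns with regard to the use of ATT in end-of-life care of cancer patients". Section 10(a) says that the general questions cover end-of-life care and the prescribing or deprescribing of "antithrombotic medication to cancer patients during end-of-life care".

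Section 15.2 prints nine general questions. Item 3 (ever having deprescribed) names cancer patients; the other eight do not. Item 2 asks how often the respondent would "prescribe antithrombotic medication upon the diagnosis of a thrombotic complication", with reference simply to a patient in end-of-life care. Item 6 is "Give an estimate of the frequency per year that you actually deprescribed antithrombotic medication in patients considered to be in end-of-life care". Items 4, 5, 8 and 9 are framed in the same way, and item 7 refers to patients at the end of life.

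The definition in section 2.2 does not supply the limit either: "A patient is considered in end-of-life care in case of a confirmatory negative response of the healthcare professional to the question" that then follows, with no mention of cancer.

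Elsewhere the restriction is written out. The last pre-registration question (15.1, item 6) asks for the "number of patients you see/treat with active cancer each year, who are considered to be in end-of-life care", and the lead-in to the case questions in 15.4 also specifies active cancer.

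**The concern.** Section 6 recruits professions whose end-of-life patients are not all cancer patients: general practitioners, nursing home physicians, geriatricians, cardiologists, neurologists and vascular surgeons, alongside oncologists and haematologists. Eligibility requires that they treat cancer patients, not that they treat only cancer patients. A respondent who takes items 2 and 4 to 9 literally will include patients without cancer.

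The effect would be uneven. An oncologist's answers would change little, a nursing home physician's possibly a great deal. Section 13 promises descriptive results with 95% confidence intervals for predefined subgroups. The documents do not list these; if they include profession or country, a difference in diagnosis mix could be reported as a difference in how cancer patients are managed. A larger sample would narrow the intervals but leave that bias in place.

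It could not be undone in the analysis, because no item asks what share of a respondent's end-of-life patients, or of those deprescribed, have cancer.

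**Working it through.** The plan gives no figure on this point, so there is nothing to reproduce. The check is a comparison of wording, followed by an illustration with assumed inputs.

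**Step 1: scope of each item, as printed.**

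| Place | Cancer named? |
|---|---|
| Section 4, objective 1 | yes |
| Section 10(a), (de)prescribing questions | yes |
| Section 15.1, item 6 | yes (active cancer) |
| Section 15.2, item 1 | no, but consistent with section 10(a) |
| Section 15.2, item 2 | no |
| Section 15.2, item 3 | yes |
| Section 15.2, items 4 to 9 | no |
| Section 15.4, lead-in | yes (active cancer) |

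So 1 of 9 items names cancer and 8 do not. Item 1 ("When do you consider a patient in end-of-life care? If the life expectancy is") is set aside: section 10(a) gives it, also without mention of cancer, as an example of the questions on end-of-life care in general. That leaves 8 − 1 = 7 items (2 and 4 to 9) whose wording is wider than the stated scope.

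**Step 2: effect on the annual counts (items 5 and 6).** Let f be the share of the patients counted who have cancer. The reported count divided by the cancer count is 1/f. The documents do not give f, so the values below are assumptions:

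- f = 0.9: 1/0.9 = 1.11
- f = 0.75: 1/0.75 = 1.33
- f = 0.5: 1/0.5 = 2
- f = 0.25: 1/0.25 = 4
- f = 0.2: 1/0.2 = 5

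For a comparison, suppose two respondents each deprescribe in 3 cancer patients a year, one with f = 0.9 and one with f = 0.25. They would report 3/0.9 = 3.3 and 3/0.25 = 12, an apparent ratio of 12/3.3 = 3.6 where the cancer counts are equal.

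**Step 3: effect on a proportion.** Let s be the cancer share of the patients a respondent has in mind, and d the rate in patients without cancer minus the rate in those with cancer. The shift is (1 − s) × d. With an assumed d of 20 percentage points:

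- s = 0.25: 0.75 × 20 = 15 points
- s = 0.5: 0.5 × 20 = 10 points
- s = 0.75: 0.25 × 20 = 5 points
- s = 0.9: 0.1 × 20 = 2 points

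If d = 0, or if respondents answer for cancer patients only (s = 1), the shift is zero.

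**Step 4: can other data repair it?** The case block (15.4) is correctly restricted, but it holds at most three cases per respondent, all chosen because deprescribing was considered. It cannot yield annual frequencies, and it has no counterpart to item 2 (starting treatment) or item 7 (discussion with colleagues). Section 11 also has it exported and analysed apart from the rest of the survey.

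**The case against.** The best reply is that context supplies the restriction. Respondents are recruited because they treat cancer patients, and their last pre-registration question is about active cancer. Item 3 names cancer patients, and a respondent who answers no skips some later questions; the skipped items are not named, but items 4 to 6 read naturally as follow-ups. The factor list for items 8 and 9 includes ECOG performance status. Section 10(a) itself illustrates the cancer-related questions with one that does not mention cancer, so the authors may use unqualified wording as shorthand. The information given to prospective participants is not in the documents and may set the scope.

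This stands as far as certainty goes. A reader might infer that the answers will describe a different population; the documents show only that the population is not fixed. Context does not settle the matter, because the restriction is written out in 15.1, in item 3 and in 15.4, and is dropped directly after item 3.

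Three further inferences go too far:

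- *That the whole flash mob result is affected.* The case block, planned for up to 2400 patients, is limited to active cancer and records both the decision and its reasons. It overlaps with item 9.
- *That the study will report impossible rates.* Dividing 15.2 item 6 by 15.1 item 6 could give, say, 12/10 = 120% where the cancer figure is 3/10, but no section plans that ratio. Items 5 and 6 use the same population wording, so their ratio to each other is at least like for like.
- *That the inflation is known to be several-fold.* The fold figures follow only from assumed shares.

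**Conclusion.** The point holds as an ambiguity in seven printed questions. Items 2 and 4 to 9 of section 15.2 do not carry the cancer restriction that objective 1 and section 10(a) state. Mixed-practice respondents may answer for all end-of-life patients, and the data collected could not show who did.

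The consequence is greatest for items 5 and 6, which ask for absolute annual numbers: inflation by 1/f, from 1.11 at f = 0.9 to 5 at f = 0.2, with f assumed throughout. For the other items the shift depends on how far practice differs between patients with and without cancer, which the documents do not address, and it may be zero. Bias in comparisons between professions or countries is possible, but neither its size nor its direction can be determined. The actual-case block and item 1 are outside the point.

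This is a free improvement: the possible bias is of unknown size, and removing it costs almost nothing.

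**What to change.** Before launch, do one of two things:

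- add *with active cancer* to items 2 and 4 to 9 of section 15.2, and change item 3 to the same term; or
- open section 15.2 with one sentence, modelled on the lead-in to 15.4, saying that the prescribing and deprescribing questions concern patients with active cancer in end-of-life care.

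Either makes these items cover the population of objective 1 and of the caseload question in 15.1, using the term that section 2.1 already defines. Item 1 can stay as it is.

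The cost is a few words in the electronic form. It needs no new items, respondents or analysis. Timing matters, because section 12 allows only seven days for data collection and the answers cannot be separated by diagnosis afterwards.
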